## **6.4 Treatment Blinding**

This is an open-label study. Therefore, after randomization, the investigator, pharmacist and patient will be aware of which treatment is administered to the patient. The investigator should, however, withhold the treatment assignment from the local pathologist interpreting the biopsies. The local pathologist will provide the investigator their interpretation for clinical management of the patient.

## **6.5 Treating the patient**

### **6.5.1 Patient numbering**

Each patient is uniquely identified in the study by a patient number. The center number for this trial will be 01. Upon signing the informed consent form, the patient is assigned a patient number by the investigator. The first patient is assigned patient number 001, and subsequent patients are assigned consecutive numbers (e.g. the second patient is assigned patient number 002, the third patient is assigned patient number 003). Therefore, the first patient is identified as 01-001 (e.g. the second patient is identified as 01-002). A patient number will not be reused. If the patient fails to be randomized for any reason, the reason for not being randomized will be entered on the Screening Log, and the Demography CRF should also be completed.

### **6.5.2 Dispensing the study drug**

Novartis will supply packs of open-label study drug Everolimus.

The study medication packaging has a 2-part label. A unique randomization number is printed on each part of this label which corresponds to the treatment arms, according to the confidential randomization list. The Research Pharmacy will identify the investigational drug to dispense to the patient using the randomization number on the label. Immediately before dispensing the investigational drug to the patient, the Research Pharmacy will detach the outer part of the label from the packaging and affix it to the source document (Drug Label Form) for that patient's unique patient number. The randomization number must also be recorded on the Randomization Number CRF.

### **6.5.3 Study drug supply, storage and tracking**

Study drugs must be received by the Research Pharmacy, handled and stored safely and properly, and kept in a secured location to which only the pharmacy staff and designated assistants have access. All study drugs should be stored according to the instructions specified on the drug labels upon receipt. Clinical supplies are to be dispensed only in accordance with the protocol.

Medication labels will be in English and comply with the legal requirements of the United States of America. They will include storage conditions for the drug.

The Research Pharmacy will maintain an accurate record of the shipment and dispensing of study drug in a drug accountability ledger per their SOPs. Patients will be asked to return all unused study drug and packaging at the end of the study or at the time of study drug discontinuation.

At the conclusion of the study, and as appropriate during the course of the study, the investigator will destroy all used and unused study drug, packaging, drug labels, per research pharmacy policy and SOP and a copy of the completed drug accountability log will be retained with study files

#### **6.5.4 Instructions for prescribing and taking the study drug**

The investigator should instruct the patient to take the study drug exactly as prescribed. All dosages prescribed and dispensed to the patient and all dose changes during the study must be recorded on the Study Drug Administration Record CRF.

Everolimus will be provided only as 0.5 mg or 0.75 mg tablets and will be packaged in boxes containing 12 strips of 10 blister packed tablets. The investigator will dispense the appropriate number of blister packed tablets to cover each visit and an additional medication in case of loss, breakage, or scheduling problems.

The investigator/the study team is responsible for instructing the patients regarding the exact dose and dosing schedule to be followed.

Medication labels will comply with the legal requirements of the United States of America and will be in English. The storage conditions for study drug will be described on the medication label.

#### **Investigational drug**

Patients will take ERL or MMF/MPA simultaneously with TAC twice daily in 12 hour intervals and on a consistent schedule with regards to time of day and relation to meals. For this study, either MMF 1,000 mg BID or MPA 720 mg BID will be allowed since MMF and MPA are considered to be therapeutically equivalent.

No grapefruit or grapefruit juice should be taken throughout the study.

### **Arms 1 and 2 (Everolimus Groups)**

Initial dosing of ERL will be 1 tablet of 0.75 mg ERL BID (1.5 mg/day) for patients randomized into either one of ERL groups. Additional medication for dose adjustments will be provided in 0.5 mg or 0.75 mg tablet strengths. The investigator is responsible for instructing the patients regarding the exact dose and dosing schedule to be followed. At Day 7, ERL will be dosed to target trough levels of 3 to 8 ng/ml. At Month 3, ERL will be dosed to target levels of 5 to 8 ng/mL. The ERL trough level should remain less than 8 ng/mL during the whole study duration.

Patients may require dose adjustments based on tolerability, individual response, changes in co-medications, or clinical condition. Dose adjustments can be made at 4-5 day intervals.

Everolimus and tacrolimus should be taken at the same time and consistently either before, during or after meals.

### **Arm 3 (MMF/MPA - Control group)**

Initial dosing of MMF/MPA will be 1000/720 mg BID (2/1.44 g/day) respectively for patients randomized into the MMF/MPA group. The dose should be adjusted for gastrointestinal intolerance and/or a decrease in WBC. For GI intolerance, the MMF/MPA dose should be reduced to 750 mg BID (1.5 g/day). If the GI intolerance persists, the dose can be reduced to 500 mg BID (1 g/day). MMF/MPA may be administered with antacids containing magnesium and aluminum hydroxides; however it is recommended that MMF/MPA and the antacid not be administered simultaneously. If neutropenia develops, dosing with MMF/MPA should be interrupted or reduced and the patient managed appropriately. The investigator is responsible for instructing the patients regarding the exact dose and dosing schedule to be followed.

MMF/MPA and TAC should be taken at the same time and consistently either before, during or after meals.

All dosages prescribed and dispensed to the patient and all dose changes during the study must be recorded on the Dosage Administration Record CRF.

The investigator should promote compliance by instructing the patient to take the study drug exactly as prescribed and by stating that compliance is necessary for the patient's safety and the validity of the study. The patient should be instructed to contact the investigator if he/she is unable for any reason to take the study drug as prescribed.

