### **MMF/MPA treatment arm 3 (SOC):**

MMF/MPA dose will be initiated as 1 g BID (2 g/day)/720 mg BID (1,440 mg/day). Adjustments should be made for adverse events including but not limited to gastrointestinal intolerance and a decrease in WBC. The tacrolimus will be initiated and adjusted to achieve a target whole blood trough concentration of 8 ng/mL to 12 ng/mL. From Month 12 on, the target tacrolimus trough level will be decreased to 6 ng/mL to 8 ng/mL. Steroids will be administered according to our standard practice.

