For Arms 1 and 2, the initial Tacrolimus dose of 0.03 mg/kg (based on ideal body weight) will be given within 24 hours of transplant. Subsequently, the target Tacrolimus trough levels will be 4 to 7 ng/ml from Day 1 to Month 3, and 2 to 5 ng/ml from Month 3 until study completion. For Arm 3, the initial dosing and adjustment will follow the institutional practice.

Patients on Arm 2 will be converted between weeks 12 and 14, after the protocol biopsy. Conversion of Tacrolimus to MMF/MPA (arm 2) will be done abruptly. On the day of conversion, MMF/MPA 1,000/720 mg will be given twice a day while no Tacrolimus will be given. In other words, there is no overlapping of Tacrolimus and MMF/MPA dosing.

For Arm 2 (after Month 3) and arm 3, MMF/MPA will be initiated at 1,000/720 mg and administered according to our standard practice in corresponding arms. Adjustment of doses may occur due to side effects, and in such cases, adjustment will follow the institutional standard practice.

All groups will be treated with corticosteroids, and prednisone will be tapered off or withdrawn according to standard practice.

[figure not shown]
For patients experiencing delayed graft function (DGF), Tacrolimus can be held up to 14 days. If this period is more than 14 consecutive days or more than two episodes of 7 days or longer, study drug discontinuation will be discussed among the study team including nephrologists. In all suspected rejection episodes, biopsy will be performed, and all patients will be treated as per our standard practice based on biopsy findings.

For patients on Arm 1 and 2 experiencing severe side effects such as complications due to delayed wound healing and mouth sores, Everolimus can be held up to 14 days. Patients who will require a prolonged discontinuation of Everolimus longer than 14 days will be withdrawn, and will be monitored as a regular follow-up until 1 month after the discontinuation. Then, patients will be monitored at a reduced follow-up schedule (Table 1).

During the 24 month study period, patients will be monitored according to the study visit schedule as listed in Table 1. The assessment to address the primary objective will be performed at month 6, 12, and 24. No interim analysis is planned. All withdrawn patients will be monitored at a reduced follow-up schedule.

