## **Everolimus and MMF/MPA guidelines for dose reductions for safety reasons:**

For patients who are unable to tolerate the protocol-specified dosing schedule, dose adjustments are permitted in order to keep the patient on study drug. Reasons for study drug dose reductions may be for example, a decrease in the white blood cell count or platelet count, an increase in cholesterol or triglyceride level, gastrointestinal intolerance or other adverse events. Severe and unremitting changes may lead to study drug discontinuation. If study medication (ERL or MMF/MPA) is interrupted for safety reasons for 2 episodes of  $\geq 7$  consecutive days, or more than 21 consecutive days, discontinuation of study medication should be discussed with the sponsor.

During the course of the trial the study drugs will be administered on a BID regimen. Study medication will not be provided to patients after they have discontinued the study.

- Everolimus 1.5 mg treatment groups
  - It is recommended to reduce the dosing from the standard 0.75 mg BID to 0.5 mg BID. The dosing should, however, always follow a BID schedule.
- MMF/MPA 2,000/1,440 mg treatment group
  - MMF/MPA dose can be adjusted for gastrointestinal intolerance or a decrease in WBC. If neutropenia develops ( $ANC < 1,300/\text{mm}^3$ ) dosing with MMF/MPA should be interrupted or reduced, appropriate diagnostic tests performed and the patient managed according to local practice.

Additional information for dose adjustments based on laboratory values or other adverse events may be found in Appendix 3.

All changes in dosing of the investigational and control drug must be recorded on the Study Drug Dosage Administration Record CRF with date and reason.

The TAC dose must be adjusted to get  $C_{0-h}$  value within the pre-specified target range: for ERL Arm 1: 4 - 7 ng/mL from Day 1 until Month 3, and 2 - 5 ng/mL starting at the Month 3 Visit; for ERL Arm 2: 4 – 7 ng/mL from Day 1 until Month 3, where the patient will be converted from TAC to MMF/MPA; for SOC arm 3: 8 - 12 ng/mL starting at Day 1 until

Month 12, and 6 – 8 ng/mL from Month 12 until study completion. If TAC is held for > 14 days, study drug should be discontinued and the patient discontinued from the study.

These changes must be recorded on the Dosage Administration Record CRF.

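### The first dose-reduction step for GI intolerance in Arm 3 (750 mg BID) is above the MPA starting dose of 720 mg BID, so for a patient on MPA it is not a reduction

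*Combined protocol and SAP*

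**What the plan says.** Section 6.5.4, under the Arm 3 heading, sets the starting doses by product: "Initial dosing of MMF/MPA will be 1000/720 mg BID (2/1.44 g/day) respectively for patients randomized into the MMF/MPA group". For gastrointestinal intolerance it then gives one figure under the joint label: "the MMF/MPA dose should be reduced to 750 mg BID (1.5 g/day"). A second, optional step follows: "If the GI intolerance persists, the dose can be reduced to 500 mg BID (1 g/day").

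Elsewhere the protocol treats the two products as a pair with different milligram doses. The synopsis has "MMF/MPA dose will be initiated as 1 g BID (2 g/day)/720 mg BID (1,440 mg/day"), and Section 6.5.5 names the arm as the "MMF/MPA 2,000/1,440 mg treatment group". Section 6.5.4 and Section 4 both treat MMF 1,000 mg BID and MPA 720 mg BID as therapeutically equivalent and allow either.

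Other provisions on dose adjustment give no figure for GI intolerance:

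- Synopsis, Arm 3: "Adjustments should be made for adverse events including but not limited to gastrointestinal intolerance and a decrease in WBC".
- Section 6.5.5: "MMF/MPA dose can be adjusted for gastrointestinal intolerance or a decrease in WBC".
- Section 4, for Arm 3 and for Arm 2 after Month 3: "Adjustment of doses may occur due to side effects, and in such cases, adjustment will follow the institutional standard practice".
- Appendix 3 lets the investigator interrupt or reduce study medication for a causally associated adverse event and names GI intolerance as an example. Its numbered guidance covers platelets, white cells, cholesterol and triglycerides.

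**The concern.** The starting doses are product-specific, but the reduction steps are not. A single milligram figure cannot serve both products when their starting doses differ by 280 mg. The 750 mg figure lies between the two: below the MMF start and above the MPA start. Read literally, the instruction raises the dose of a patient who is not tolerating MPA.

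What is at stake is a dosing rule for a permitted control product, in a situation the protocol itself foresees. The wording of the first step is directive. This is also the only visible place that gives numeric steps for GI intolerance. Arm 2 patients start MMF/MPA at Month 3 and have no numeric GI steps of their own, so site staff might turn to the same sentence for them.

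**Working it through.** **Inputs**

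- Starting doses: MMF 1,000 mg BID and MPA 720 mg BID (Section 6.5.4, Arm 3; the synopsis agrees).
- Step 1: 750 mg BID. Step 2: 500 mg BID (Section 6.5.4, Arm 3).
- Equivalence: 1,000 mg MMF to 720 mg MPA (Sections 4 and 6.5.4), a ratio of 720/1000 = 0.72.

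**Reproducing the printed daily totals** (daily dose = 2 × BID dose)

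- MMF start: 2 × 1,000 = 2,000 mg = 2 g/day.
- MPA start: 2 × 720 = 1,440 mg = 1.44 g/day.
- Step 1: 2 × 750 = 1,500 mg = 1.5 g/day.
- Step 2: 2 × 500 = 1,000 mg = 1 g/day.

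All four match the text. The 750 mg figure agrees with its own daily total, so a misread digit does not explain the mismatch.

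**Change from the starting dose** (step ÷ start − 1)

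| Step | MMF (start 1,000 mg BID) | MPA (start 720 mg BID) |
|---|---|---|
| 750 mg BID | 750/1000 − 1 = −25% | 750/720 − 1 = +4.2% |
| 500 mg BID | 500/1000 − 1 = −50% | 500/720 − 1 = −30.6% |

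For MPA at Step 1 the difference is 750 − 720 = +30 mg per dose, and 2 × 30 = +60 mg/day (1.44 to 1.50 g/day).

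**On the MMF scale.** At the protocol's own ratio, MPA 750 mg BID corresponds to 750/0.72 = 1,042 mg MMF BID, or 2.08 g/day. That is above the MMF starting dose.

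**MPA doses that match the MMF steps**

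- Step 1: 750 × 0.72 = 540 mg BID (1.08 g/day, −25%).
- Step 2: 500 × 0.72 = 360 mg BID (0.72 g/day, −50%).

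These two MPA figures are derived here; the protocol does not state them.

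**The case against.** The strongest reply is that this is an editorial slip with little practical effect. The two steps are exactly 75% and 50% of the MMF dose, and Section 6.1 names only MMF as the control drug, so the sentence looks like MMF text to which MPA was later added. The instruction is to reduce, and no reasonable prescriber would raise a dose under it. Section 4 already sends side-effect adjustments in this arm to institutional practice, which is one of the remedies proposed below. The synopsis, Section 6.5.5 and Appendix 3 also leave room for judgement. Finally, Appendix 3 refers to a dose-reduction table that is not visible in the text available, and it could contain an MPA step.

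Most of this stands, and it sets the weight of the point. Practical harm is likely to be small, and Section 4 deserves credit as an existing fallback. The objection about Step 2 also stands: 500 mg BID is a genuine MPA reduction, and nothing in the protocol requires the two products to be cut by the same percentage. The smaller cut is therefore not counted as an error.

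None of it makes the Step 1 sentence right. The general provisions give no MPA figure and do not override a directive one. The missing table is cited for platelet and white-cell reductions. If it did hold an MPA step, that would soften the consequence but leave the printed figure in Section 6.5.4 uncorrected.

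**Conclusion.** The concern holds, as a minor one. For a patient on MPA, the first GI-intolerance step in Section 6.5.4 is 30 mg per dose (60 mg/day, 4.2%) above the starting dose and cannot be followed as a reduction. This rests only on figures printed in the protocol.

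How many patients could meet the problem cannot be calculated, because the protocol gives neither the MMF/MPA split nor an expected rate of GI intolerance. In Arm 3 the number lies between 0 (everyone on MMF, or no intolerance) and the 16 patients planned. The statement that no MPA step appears elsewhere applies to the visible text only. The trial's design, sample size, power and analyses are not affected.

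**What to change.** In the Arm 3 paragraph of Section 6.5.4, label 750 mg BID and then 500 mg BID as MMF doses. For MPA, do one of the following:

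- give paired steps at the protocol's 1000:720 ratio, that is 540 and then 360 mg BID, or the nearest feasible tablet dose, since the protocol does not state MPA tablet strengths; or
- state there that MPA reductions follow institutional practice, with a cross-reference to Section 4.

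The cost is one sentence of protocol wording, with no change to design, sample size or analysis.

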#### **6.5.5 Permitted study drug dose adjustments and interruptions**

For patients who are unable to tolerate the protocol-specified dosing scheme, dose adjustments and interruptions are permitted in order to keep the patient on study drug. The following guidelines should be followed:

#### **Therapeutic drug monitoring**

Blood for ERL trough levels will be obtained from all patients at the time points indicated in Table 7-1. In the ERL group, therapeutic drug monitoring (TDM) will be mandatory throughout the study.

## **On Day 7 after initiation of Everolimus treatment**

For Arm 1 and Arm 2 (ERL groups), the 0.75 mg BID dose will be increased if the ERL trough level is < 3 ng/mL, and reduced if the ERL trough level is > 8 ng/mL until Month 3. Starting at Month 3, ERL will be dosed to target levels of 5 to 8 ng/mL. The dose will be increased if the ERL trough level is < 5 ng/mL, and reduced if the ERL trough level is > 8 ng/mL.

Everolimus dose adjustments should be made on results of the trough levels from the hospital laboratory. Tacrolimus dose adjustments should be made based on the results of the trough levels done at the local laboratory. Tacrolimus trough levels will also be run at the hospital laboratory for purposes of the protocol.

Follow-up ERL and TAC trough levels should be measured 5-7 days after any dose adjustment to ERL or TAC to ensure that the recommended troughs are achieved.

## **Everolimus and MMF/MPA guidelines for dose reductions for safety reasons:**

For patients who are unable to tolerate the protocol-specified dosing schedule, dose adjustments are permitted in order to keep the patient on study drug. Reasons for study drug dose reductions may be for example, a decrease in the white blood cell count or platelet count, an increase in cholesterol or triglyceride level, gastrointestinal intolerance or other adverse events. Severe and unremitting changes may lead to study drug discontinuation. If study medication (ERL or MMF/MPA) is interrupted for safety reasons for 2 episodes of  $\geq 7$  consecutive days, or more than 21 consecutive days, discontinuation of study medication should be discussed with the sponsor.

During the course of the trial the study drugs will be administered on a BID regimen. Study medication will not be provided to patients after they have discontinued the study.

- Everolimus 1.5 mg treatment groups
  - It is recommended to reduce the dosing from the standard 0.75 mg BID to 0.5 mg BID. The dosing should, however, always follow a BID schedule.
- MMF/MPA 2,000/1,440 mg treatment group
  - MMF/MPA dose can be adjusted for gastrointestinal intolerance or a decrease in WBC. If neutropenia develops ( $ANC < 1,300/\text{mm}^3$ ) dosing with MMF/MPA should be interrupted or reduced, appropriate diagnostic tests performed and the patient managed according to local practice.

Additional information for dose adjustments based on laboratory values or other adverse events may be found in Appendix 3.

All changes in dosing of the investigational and control drug must be recorded on the Study Drug Dosage Administration Record CRF with date and reason.

The TAC dose must be adjusted to get  $C_{0-h}$  value within the pre-specified target range: for ERL Arm 1: 4 - 7 ng/mL from Day 1 until Month 3, and 2 - 5 ng/mL starting at the Month 3 Visit; for ERL Arm 2: 4 – 7 ng/mL from Day 1 until Month 3, where the patient will be converted from TAC to MMF/MPA; for SOC arm 3: 8 - 12 ng/mL starting at Day 1 until

Month 12, and 6 – 8 ng/mL from Month 12 until study completion. If TAC is held for > 14 days, study drug should be discontinued and the patient discontinued from the study.

These changes must be recorded on the Dosage Administration Record CRF.

### **6.5.6 Rescue medication**

#### **Treatment of acute rejection episodes**

In all suspected rejection episodes, regardless of initiation of anti-rejection treatment, a graft core biopsy must be performed within 48 hours. Biopsies will be read by pathologists at MGTI according to the Banff criteria (Appendix 2). Determination of the need for treatment will be according to our pathologists' findings and the overall clinical presentation of rejection. All episodes of acute rejection should be treated as per institutional standard practice, for example bolus steroids as first line and anti-T-cell antibody for steroid resistant rejections.

The local pathologist will remain blinded to the patient treatment. The results of the biopsy read by the pathologists will be listed on the Kidney Allograft Biopsy CRF and will be used for patient management of acute rejection. A treated BPAR will be defined as a biopsy graded IA, IB, IIA, IIB, or III. The protocol treatment assignment should not be disclosed to the pathologists.

Since patient management is based on local readings, for the analysis of the primary efficacy endpoint the pathologists' biopsy readings will be used. For the analysis of secondary efficacy endpoints and for sensitivity analysis of the primary endpoint, the pathologists' readings will be utilized.

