#### **7.4.2 Treated Biopsy Proven Acute Rejection**

Renal biopsies will be collected for all cases of suspected acute rejection. For all suspected rejection episodes, regardless of initiation of anti-rejection treatment, a graft core biopsy must be performed within 48 hours. Biopsies will be read by hospital pathologists in accordance with institutional practice. The results of the biopsy will be listed on the Kidney Allograft Biopsy CRF. The results will be used for patient management for acute rejection and for the efficacy analysis. A treated BPAR will be defined as a biopsy graded IA, IB, IIA, IIB, or III and which is treated with anti-rejection therapy.

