## Appendix 2: Banff '97 Classification of renal allograft rejection

### Banff '97 diagnostic categories for renal allograft biopsies

1. Normal
2. Antibody-mediated rejection - Rejection demonstrated to be due, at least in part, to documented anti-donor antibody ("suspicious for" if antibody not demonstrated)
  - Type I – ATN – like – C4d+, minimal inflammation
  - Type II – Capillary-margination and/or thromboses, Ig and/or C4d+
  - Type III – Arterial – v3, C4d+
3. Borderline changes ("suspicious" for acute cellular rejection). This category is used when no intimal arteritis is present, but there are foci of mild tubulitis (1 to 4 mononuclear cells/tubular cross section) and at least i1.
4. Acute/active rejection
  - TYPE IA - Cases with significant interstitial infiltration ( $> 25\%$  of parenchyma affected) and foci of moderate tubulitis ( $> 4$  mononuclear cells/tubular cross section or group of 10 tubular cells).
  - TYPE IB - Cases with significant interstitial infiltration ( $> 25\%$  of parenchyma affected) and foci of severe tubulitis ( $> 10$  mononuclear cells/tubular cross section or group of 10 tubular cells).
  - TYPE IIA - Cases with mild to moderate intimal arteritis (v1).
  - TYPE IIB - Cases with severe intimal arteritis comprising  $> 25\%$  of the luminal area (v2).
  - TYPE III - Cases with "transmural" arteritis and/or arterial fibrinoid change and necrosis of medial smooth muscle cells (v3 with accompanying lymphocytic inflammation).
5. Chronic/sclerosing allograft nephropathy\*\*
  - GRADE I (Mild) Mild interstitial fibrosis and tubular atrophy without (a) or with (b) specific changes suggesting chronic rejection.
  - GRADE II (Moderate) Moderate interstitial fibrosis and tubular atrophy (a) or (b).
  - GRADE III (Severe) Severe interstitial fibrosis and tubular atrophy and tubular loss (a) or (b).
6. Other, specify (changes not considered to be due to rejection, i.e., post-transplant lymphoproliferative disorder, nonspecific changes, acute tubular necrosis, etc.)

\*The recommended format of report is a descriptive narrative signet followed by numerical codes (Banff 97) in parentheses. Categorization should in the first instance be based solely on pathologic changes, and then integrated with clinical data as a second step. More than one diagnostic category may be used if appropriate.

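### Treated BPAR, a component of the primary composite, is defined by grade alone in 6.5.6 but by grade plus treatment in 7.4.2, and no planned analysis tests the difference

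*Combined protocol and SAP*

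**What the plan says.** **Definition.** Section 6.5.6 (treatment of acute rejection episodes) reads "A treated BPAR will be defined as a biopsy graded IA, IB, IIA, IIB, or III" and stops there. Section 7.4.2 reads "A treated BPAR will be defined as a biopsy graded IA, IB, IIA, IIB, or III and which is treated with anti-rejection therapy". Section 10.4 lists BPAR among the efficacy variables without the word treated. Sections 3.1, 10.4.1 and 10.4.4 use treated BPAR in the composite. No section says which definition governs.

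**Readings.** On the primary endpoint, section 6.5.6 says "for the analysis of the primary efficacy endpoint the pathologists' biopsy readings will be used". The next sentence says "For the analysis of secondary efficacy endpoints and for sensitivity analysis of the primary endpoint, the pathologists' readings will be utilized". The only readers named in the document are the local pathologists, who are kept unaware of treatment.

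**Treatment decision and blinding.** Section 6.5.6 bases the need for treatment on the pathology and the clinical picture together, and then says that all acute rejection episodes should be treated according to institutional practice. Section 6.4 says that "after randomization, the investigator, pharmacist and patient will be aware of which treatment is administered to the patient".

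**Biopsies.** Section 7.4.3 plans biopsies at Months 3, 12 and 24 for all patients. Section 6.5.8 limits them to patients who agree, and Table 7-1 allows a scheduled biopsy to be left out if a clinically indicated one came first.

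**The concern.** Biopsies taken by calendar can show grade IA or higher in a patient with no clinical signs. If that patient is not given anti-rejection therapy, the two definitions classify the same patient differently, and the primary failure count depends on which section the analyst follows. Because the trial is open label, that choice could be made after outcomes by arm are known.

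The two definitions also differ in their exposure to bias. Under 7.4.2 an event requires a decision to treat, made by clinicians who know the arm. Under 6.5.6 the event rests on a blinded reading. The arms differ by design in tacrolimus exposure (Table 6-1), so a different readiness to treat a borderline clinical picture is plausible, although the documents do not indicate its direction. One would look to a sensitivity analysis to show whether this matters, but none of those planned addresses it.

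**Working it through.** There is no stated figure to reproduce. The check is a comparison of sections, followed by simple arithmetic on the size of one reclassification.

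**Step 1. Classification under each definition**

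| Biopsy result | Anti-rejection therapy | 6.5.6 | 7.4.2 |
|---|---|---|---|
| IA to III | given | event | event |
| IA to III | not given | event | no event |
| below IA | either | no event | no event |

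The definitions part company only in the second row.

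**Step 2. Can the second row occur?** It needs a graded biopsy without treatment. Calendar biopsies (7.4.3, Table 7-1) supply readings that were not prompted by suspicion, and 6.5.6 makes the need for treatment a judgement that includes the clinical picture. So it can occur. How often is not stated.

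**Step 3. Does any planned analysis vary the definition?**

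- 6.5.6: the sensitivity analysis of the primary endpoint uses the pathologists' readings, as does the primary analysis. No second or central reader is named, so there is no change of readings to test.
- 10.1: repeats efficacy in the Per Protocol Set and Safety Set. This varies the population.
- 10.4.3: complete-case and missing-data analyses if imputed data exceed 5%. This varies missing-data handling.
- 10.4.4: Cochran-Mantel-Haenszel, logistic regression, Kaplan-Meier and log-rank. This varies the method.

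None of these varies the definition of the BPAR event.

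**Step 4. Size of one reclassification.** Input: 16 patients per arm (6.3 and 10.6), all assumed to be in the Full Analysis Set. For k graded but untreated patients in an arm with no other composite event, the arm's failure rates under the two definitions differ by k/16.

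- k = 0: 0 points
- k = 1: 1/16 = 6.25 points
- k = 2: 2/16 = 12.5 points
- k = 3: 3/16 = 18.75 points

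The values of k are assumptions; the documents do not support any one of them.

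**Step 5. Can one patient matter to a test?** Fisher's exact test is named in the synopsis and in 10.7. The counts below are illustrative, because the plan gives no event rates. Two-sided p, 16 per arm:

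- 2/16 v 8/16: p = 0.054; 2/16 v 9/16: p = 0.023
- 1/16 v 6/16: p = 0.083; 1/16 v 7/16: p = 0.037

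At some plausible counts a single reclassified patient crosses 0.05. At many others it does not.

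**The case against.** The strongest reply is that 6.5.6 is shorthand. The term being defined there is itself treated BPAR, the subsection concerns treatment, and shortly before the definition it says that all acute rejection episodes should be treated. The section devoted to the endpoint, 7.4.2, states the condition in full, and the objectives and analysis sections nearly all say treated. If grade always led to treatment, the two definitions would coincide.

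Most of this stands, and it makes 7.4.2 the natural choice. It narrows the gap without closing it. The treat-all sentence follows one that makes need for treatment a judgement, and the added clause in 7.4.2 would do no work if every graded biopsy were treated.

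Several stronger readings are tempting, but the documents do not support them:

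- **The sensitivity result must equal the primary result.** Section 6.5.6 says only which readings are used, not that nothing else changes. The missing-data analyses in 10.4.3 could give different results from the same readings.
- **Treated BPAR is the main component.** No component rates are given, and two statements of the objective (the synopsis and the one closing the Background) also include delayed graft function.
- **Every patient has three protocol biopsies.** Section 6.5.8 and the biopsy note in Table 7-1 allow for fewer.
- **Leaving out antibody-mediated rejection is an error.** Appendix 2 lists it as a separate category ("Antibody-mediated rejection - Rejection demonstrated to be due, at least in part, to documented anti-donor antibody"). That category has its own Type III, and more than one category may be assigned, so its exclusion is not certain. Whether to count it is a choice of scope.

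**Conclusion.** The concern holds as a conflict of definition with no analysis to show its effect. Sections 6.5.6 and 7.4.2 give different rules for a component of the primary endpoint, and section 10.4 gives a third, looser wording. The sensitivity analysis in 6.5.6 tests nothing through a change of readings, because there is only one set.

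The size is 6.25 percentage points of an arm's failure rate per graded but untreated patient. This assumes 16 analysed per arm and no other composite event in that patient. The number of such patients is unknown and may be zero, so no particular bias or shift can be claimed. The unblinded treatment decision enters the endpoint only under 7.4.2, and its direction cannot be inferred. Pilot status limits the consequences, but the plan still declares a primary efficacy comparison, and its event should be fixed before the data are analysed.

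**What to change.** 1. Use one definition in 6.5.6, 7.4.2 and 10.4: Banff grade IA to III and treated with anti-rejection therapy. This matches the endpoint's name and its use in 3.1, 10.4.1 and 10.4.4.
2. Replace the same-readings sensitivity analysis in 6.5.6 with one that counts any blinded reading of grade IA to III, treated or not, on a for-cause or protocol biopsy. This removes the treatment decision from the event. State its limit: for-cause biopsies are still triggered by clinicians who know the arm.
3. Optionally, add a tabulation that also counts treated antibody-mediated rejection. This is a scope choice and not needed to resolve the conflict.

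The cost of items 1 and 2 is a wording amendment and one extra tabulation. No new biopsies, readers or visits are needed. Biopsy results and rejection episodes are already recorded on the biopsy and rejection CRFs (7.4.1 to 7.4.3), and drug therapy on the immunosuppressive and concomitant medication CRFs (6.5.7.9 and 7.3). The change concerns how events are counted, not how patients are managed.
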